12.3. Missing data

Any missing data will be dealt with, if needed, using methods appropriate to the conjectured missing mechanism and level of missing.

12.4. Interim analyses

The analysis on the primary endpoint of reactogenicity, i.e. solicited AEs will be carried out once the 7-day e-diary data become available. The analysis on the secondary endpoint of immunogenicity will be carried out when the D70 immunogenicity data, i.e. 14 days post boost, become available. The interim analyses will provide evidence for policy making as to the recommendation on the second dose of COVID-19 vaccine among adolescents. The interim analyses will be carried out once the data is cleaned and the Study Analysis Plan is signed off. There will be no stopping rule for this interim analysis and the analysis will not affect the continuation of the trial.

After further discussion with Joint Committee on Vaccination and Immunisation (JCVI), the study team decided to carry out another interim analysis in December 2021. In this analysis, we will review the sero-status pre-boost as well as all the available immunogenicity data. These data will be shared with JCVI only to support decision making on boost dose among people aged 12-17. This interim analysis will be descriptive.

On 29th November 2021, the JCIV recommended that all 12 to 15 year-olds should be offered a second dose of BNT162b2 vaccine before reviewing the planned interim analysis in December 2021. The study design was amended to focus on immune response to full dose and one third dose of BNT162b2. The planned analysis in December will still be conducted and results will be

presented to JCVI to update their recommendation. The study's recruitment and sample size will then be reviewed on the basis of this analysis after discussing with JCIV, TSC and DSMB.

13. DATA MANAGEMENT

The Chief Investigator will be responsible for all data that accrues from the study.

13.1. Access to Data & Data Protection

Direct access will be granted to authorised representatives from the Sponsor, host institution and the regulatory authorities to permit trial-related monitoring, audits and inspections. The study protocol, documentation, data and all other information generated will be held in strict confidence. No information concerning the study or the data will be released to any unauthorised third party, without prior written approval of the sponsor.

13.2. Data Recording

All study data including participant diary will be recorded directly into an EDC system (REDCap) or onto a paper source document for later entry into EDC if direct entry is not available. This includes safety, laboratory and outcome data. Any additional information that needs recording, but is not relevant for the eCRF (e.g signed consent forms) will be recorded on separate paper source documents. All documents will be stored safely and securely in confidential conditions. The EDC online data is stored on University of Oxford servers.

All participant reported adverse event data (both solicited & unsolicited) will be entered onto electronic diary cards (e-diaries) for a maximum of 28 days following administration of the IMP. The e-diary provides a full audit trail of edits and will be reviewed at time-points as indicated in the schedule of events. Any adverse event continuing beyond the period of the diary will be copied into the eCRF as required for safety review.

The participants will be identified by a unique trial specific number and code in any database. The name and any other identifying detail will NOT be included in any trial data electronic file, with the exception of the electronic diaries, for which consent will be obtained to store the participant email address for quality control purposes. Only site research staff and sponsor data managers have access to view the email address.

The EDC system (CRF data) uses a relational database (MySQL/ PostgreSQL) via a secure web interface with data checks applied during data entry to ensure data quality. The database includes a complete suite of features which are compliant with GCP, EU and UK regulations and

Sponsor security policies, including a full audit trail, user-based privileges, and integration with the institutional LDAP server. The MySQL and PostgreSQL database and the webserver will both be housed on secure servers maintained by the University of Oxford IT personnel. The servers are in a physically secure location in Europe. Backups will be stored in accordance with the IT department schedule of daily, weekly, and monthly retained for one month, three months, and six months, respectively. The IT servers provide a stable, secure, well-maintained, and high-capacity data storage environment. REDCap is a widely-used, powerful, reliable, well-supported system. Access to the study's database will be restricted to members of the study team by username and password.

13.3. Record keeping

The Investigators will maintain appropriate medical and research records for this trial, in compliance with GCP and regulatory and institutional requirements for the protection of confidentiality of volunteers. The Chief Investigator, co-Investigators and clinical research nurses will have access to records. The Investigators will permit authorised representatives of the Sponsor(s) and Host institution, as well as ethical and regulatory agencies to examine (and when required by applicable law, to copy) clinical records for the purposes of quality assurance reviews, audits and evaluation of the study safety and progress.

Following completion of the study, identifiable information such as contact details will be stored for a minimum of 5 years and until the youngest participant turns 21 years old. This includes storage of consent forms. Storage of these data will be reviewed every 5 years and files will be confidentially destroyed if storage is no longer required. Considerations at the time of this review will include the value of retaining this information for participant safety (e.g. to inform participants of unexpected safety signals emerging from post-licensing surveillance), as a resource for the participants (e.g. if they wish to check which vaccines they have received in the study) and any regulatory requirements. De-identified research data maybe be stored indefinitely. If volunteers consent to be contacted for future research, a record of this consent will be recorded, retained and stored securely and separately from the research data. If volunteers consent to have their samples stored and used in future research, information about their consent form will be retained and stored securely as per Biobanking procedures and SOP.

13.4. Source data and Case Report Forms (CRFs)

All protocol-required information will be collected in CRFs designed by the Investigator. All source documents will be filed in the participant file. Source documents are original documents,

data, and records from which the participant CRF data are obtained. For this study, these will include, but are not limited to, volunteer consent form, blood results, GP response letters, laboratory records, diaries, medical records and correspondence. In the majority of cases, CRF entries will be considered source data as the CRF is the site of the original recording (i.e. there is no other written or electronic record of data). In this study this will include, but is not limited to medical history, medication records, vital signs, physical examination records, urine assessments, adverse event data and details of vaccinations. All source data and participant files will be stored securely.

To prevent withdrawal of a participant due to relocation, if there is a nearby participating site and with the consent of the participant, copies of relevant participant research records (such as ICF, paper source documents) will be transferred to the local site using secure email addresses such as nhs.net or by password protected sheets. The electronic research data stored on REDCap will also be transferred to the new site. The original records will be retained by the recruiting site.

13.5. Data Quality

Data collection tools will undergo appropriate validation to ensure that data are collected accurately and completely. Datasets provided for analysis will be subject to quality control processes to ensure analysed data is a true reflection of the source data.

Trial data will be managed in compliance with local data management SOPs. If additional, study specific processes are required, an approved Data Management Plan will be implemented

14. Quality Assurance Procedures

14.1. Risk Assessment

The trial will be conducted in accordance with the current approved protocol, GCP, relevant regulations and standard operating procedures. A risk assessment and monitoring plan will be prepared before the study opens and will be reviewed as necessary over the course of the trial to reflect significant changes to the protocol or outcomes of monitoring activities.

14.2. Monitoring

Monitoring will be performed according to Good Clinical Practice (GCP) by an external monitor. Following written SOPs, the monitors will verify that the clinical trial is conducted and data are generated, documented and reported in compliance with the protocol, GCP and the applicable regulatory requirements. The investigator sites will provide direct access to all trial related source

data/documents and reports for the purpose of monitoring and auditing by the Sponsor or the Host institution and inspection by local and regulatory authorities

14.3. Trial committees

14.3.1. Trial Steering Committee

A Trial Steering Committee will be formed to oversee the study, and advise the Study Management Committee on key issues of study conduct, including, but not limited to, study pauses due to safety concerns on the advice of the DSMB.

14.3.2. Safety Monitoring Committee

A Data Safety Monitoring Board (DSMB) will be convened. The DSMB will evaluate frequency of events, safety and efficacy data as specified in the DSMB charter. The DSMB will make recommendations concerning the conduct, continuation or modification of the study for safety reasons to the Trial Steering Committee.

The DSMB will review SAEs or AESIs deemed possibly, probably or definitively related to study interventions. The DSMB will be notified within 24 hours of the Investigators' being aware of their occurrence. The DSMB can recommend placing the study on hold if deemed necessary following a study intervention-related SAE.

14.3.3. Study Management Committee

Consists of the site Investigators and the Laboratory lead for Public Health England.

15. PROTOCOL DEVIATIONS

A trial related deviation is a departure from the ethically approved trial protocol or other trial document or process (e.g. consent process or IMP administration) or from Good Clinical Practice (GCP) or any applicable regulatory requirements. Deviations from the protocol will be documented in a protocol deviation form according to SOP OVC027 and filed in the trial master file.

These will be managed as per SOP OVC027.

16. SERIOUS BREACHES

The Medicines for Human Use (Clinical Trials) Regulations contain a requirement for the notification of "serious breaches" to the MHRA within 7 days of the Sponsor becoming aware of the breach.

A serious breach is defined as “A breach of GCP or the trial protocol which is likely to affect to a significant degree –

(a) the safety or physical or mental integrity of the subjects of the trial; or

(b) the scientific value of the trial”.

In the event that a serious breach is suspected the Sponsor must be contacted within 1 working day. In collaboration with the CI the serious breach will be reviewed by the Sponsor and, if appropriate, the Sponsor will report it to the REC committee, Regulatory authority and the relevant NHS host organisation within seven calendar days.

17. ETHICAL AND REGULATORY CONSIDERATIONS

17.1. Declaration of Helsinki

The Investigator will ensure that this trial is conducted in accordance with the principles of the Declaration of Helsinki.

17.2. Guidelines for Good Clinical Practice

The Investigator will ensure that this trial is conducted in accordance with relevant regulations and with Good Clinical Practice.

17.3. Approvals

Following Sponsor approval, the protocol, informed consent form, participant information sheet and any proposed advertising material will be submitted to an appropriate Research Ethics Committee (REC), HRA (where required), regulatory authorities (MHRA in the UK), and host institution(s) for written approval. No amendments to this protocol will be made without consultation with, and agreement of, the Sponsor.

The Investigator is responsible for ensuring that changes to an approved trial, during the period for which regulatory and ethical committee(s) approval has already been given, are not initiated without regulatory and ethical committee(s) review and approval except to eliminate apparent immediate hazards to the subject (i.e. as an Urgent Safety Measure).

17.4. Other Ethical Considerations

First degree family members of the study team are not eligible for inclusion in the trial given the potential for them to be unblinded to the vaccine the participant has received, and for this to influence completion of reactogenicity diaries.

17.5. Reporting

The CI shall submit once a year throughout the clinical trial, or on request, an Annual Progress Report to the REC, HRA (where required), host organisation, funder (where required) and Sponsor. In addition, an End of Trial notification and final report will be submitted to the MHRA, the REC, host organisation and Sponsor.

17.6. Transparency in Research

Prior to the recruitment of the first participant, the trial will have been registered on a publicly accessible database. Results will be uploaded to the European Clinical Trial (EudraCT) Database within 12 months of the end of trial declaration by the CI or their delegate. Where the trial has been registered on multiple public platforms, the trial information will be kept up to date during the trial, and the CI or their delegate will upload results to all those public registries within 12 months of the end of the trial declaration.

17.7. Participant confidentiality

The study will comply with the UK General Data Protection Regulation (GDPR) and Data Protection Act 2018, which require data to be de-identified as soon as it is practical to do so. The processing of personal data of participants will be minimised by making use of a unique participant study number only on all study documents and any electronic database(s), with the exception of informed consent forms, participant ID log, electronic diaries and any other documents required for participant management. All documents will be stored securely and only accessible by study staff and authorised personnel. The study staff will safeguard the privacy of participants' personal data. A separate confidential file containing identifiable information will be stored in a secured location in accordance with the current data protection legislation.

17.8. Expenses and Benefits

Participants will be offered £10 reimbursement per visit towards travel and expenses. This may be in the form of gift cards/vouchers. Reimbursement may not be given at each visit (for example, we may give a £20 voucher at every other visit). The exact arrangements for reimbursement may vary between sites.

18. FINANCE AND INSURANCE

18.1. Funding

The study is funded by the UK Government through the National Institute for Health Research (NIHR).

18.2. Insurance

The University has a specialist insurance policy in place which would operate in the event of any participant suffering harm as a result of their involvement in the research (Newline Underwriting Management Ltd, at Lloyd's of London). NHS indemnity operates in respect of the clinical treatment that is provided and for the conduct of the research at NHS sites.

18.3. Contractual arrangements

Appropriate contractual arrangements will be put in place with all third parties.

19. PUBLICATION POLICY

The Investigators will be involved in reviewing drafts of the manuscripts, abstracts, press releases and any other publications arising from the study. Data from the study may also be used as part of a thesis for a PhD or MD.

20. DEVELOPMENT OF A NEW PRODUCT / PROCESS OR THE GENERATION OF INTELLECTUAL PROPERTY

Ownership of IP generated by employees of the University vests in the University. The University will ensure appropriate arrangements are in place as regards any new IP arising from the trial.

23. APPENDIX A: SCHEDULE OF PROCEDURES

Study timeline	Screening	D0	D56	D14 post boost	D28 post boost	D132 post boost	D236 post boost
Study window		Within 120 days of screening	Day 56–70 post prime vaccine at D0 or Day 56 + post prime vaccination in community	Day 12-17 Post D56	Day 28-42 post D56	Day 112-152 post D56	Day 224-252 post D56
Pre - screening online consent	X*						
Informed consent	X	X					
Medical history	X	X					
Interim medical history		X	X	X	X	X	X
Physical examination (as required)	(X)	(X)	(X)	(X)	(X)	(X)	(X)
Urine test (Pregnancy) (if required)		(X)**	X				
COVID-19 vaccination		(X)**	X				

COVID-19 immunogenicity bloods		(X)**	X	X	X	X	X
Troponin and NT-proBNP blood test		(X)**	X	X	X		
Saliva and nasal fluid test (if participant consents)		(X)**	X	X			
Diary review			X	X	X		
SAE/AESI check			X	X	X	X	X

* Pre - screening online consent. Restricted to taking a limited medical history online, contacting the GP for further medical record if required and telephone screening visit(s)

**Procedures performed only if prime dose administered in the study

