3. SYNOPSIS

Trial Title	A single-blind, randomised, phase II multi-centre study to determine reactogenicity and immunogenicity of heterologous prime/boost COVID-19 vaccine schedules in adolescents (COMCOV-3)
Internal ref. no. (or short title)	Comparing COVID-19 Vaccine Schedule Combinations in adolescents (Com-COV3)
Trial registration	EudraCT: 2021-004267-27 ISRCTN: 12348322
Sponsor	University of Oxford, Clinical Trials and Research Governance, Joint Research Office, [name], United Kingdom

Funder	UK Vaccine Task Force (VTF) National Institute Health Research (NIHR) Novavax (Vaccine supply)		
Clinical Phase	Phase II		
Trial Design	Single-blind, randomised homologous/heterologous-boost vaccine administration study using standard and/or fractional doses		
Trial Participants	Adolescents aged 12 to 16 years (inclusive)		
Sample Size	A total of up to 270 (+ up to an additional 10%) participants will be enrolled. A participant is considered enrolled at the time they receive a vaccine in this study		
Planned Trial Period	Approximately 26 or 34 weeks per participant Total trial period approximately 10 months		
	Objectives	Outcome Measures	Timepoint(s)
Primary	To evaluate the reactogenicity of heterologous boost at least 8 weeks following BNT162B2 prime vaccine administered to adolescents.	Solicited reactions systemic	7 days after booster immunisation
Secondary	To assess safety of heterologous boost COVID-19 vaccines	Serious adverse events Adverse events of special interest	Throughout the study
	To characterise immunogenicity of heterologous & homologous boost schedules	Anti-spike immunoglobulins	D0*, 56 post prime D 14, 28, 132, 236 post boost
		Anti-nucleocapsid immunoglobulins	D0*, 56 post prime D132, 236 post boost
		Cellular immune responses by ELISpot	D0*, 56 post prime D 14, 132, 236 post boost
To assess reactogenicity and safety of heterologous and	Solicited local reactions	7 days after prime* and boost immunisation	

	homologous boost schedules of COVID-19 vaccines	Unsolicted reactions	28 days after prime* and boost immunisation
	To evaluate immunogenicity, safety and reactogenicity of COVID-19 vaccines in participants sero-positive for SARS-CoV-2 nucleocapsid IgG at enrolment, compared with seronegative	Immunogenicity, safety & reactogenicity endpoints as outlined above	Timepoints as outlined above

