6. OBJECTIVES AND OUTCOME MEASURES

	Objectives	Outcome Measures	Timepoint(s)
Primary	To evaluate the reactogenicity of heterologous boost at least 8 weeks following BNT162B2 prime vaccine administered to adolescents.	Solicited reactions systemic	7 days after boost immunisation
Secondary	To assess safety of heterologous boost COVID-19 vaccines	Serious adverse events Adverse events of special interest	Throughout the study
	To characterise immunogenicity of heterologous & homologous boost schedules	Anti-spike immunoglobulins	D0*, 56, post prime D 14, 28, 132, 236 post boost
		Anti-nucleocapsid immunoglobulins	D0*, 56 post prime D132, 236 post boost
		Cellular immune responses by ELISpot	D0*, 56 post prime

			D 14, 132, 236 post boost
	To assess reactogenicity and safety of heterologous and homologous boost schedules of COVID-19 vaccines	Solicited local reactions	7 days after prime* and boost immunisation
		Unsolicited reactions	28 days after prime* and boost immunisation
	To evaluate immunogenicity, safety & reactogenicity of COVID-19 vaccines in participants seropositive for SARS-CoV-2 nucleocapsid IgG at enrolment, compared with seronegative	Immunogenicity, safety & reactogenicity endpoints as outlined above	Timepoints as outlined above
Exploratory	To assess incidence of SARS-CoV-2 infection in participants receiving heterologous & homologous prime/boost schedules	Self-reported SARS-CoV-2 infection, from community testing	Throughout the study
	To further characterise the blood antibody response	Neutralizing and Functional antibody assays	D0*, 56 post prime D 14, 28, 132, 236 post boost
	To characterise and compare the mucosal immune response to immunisation with homologous and heterologous COVID-19 vaccines using nasal fluid (collected using SAM-strips) and saliva samples	IgA & IgG ELISA and exploratory immunological assays	D0*, 56 post prime D14 post boost
	To determine normal ranges of markers of cardiac muscle damage in adolescents, and to assess change post-immunisation	High sensitivity troponin and N-terminal pro B-type natriuretic peptide (NT-proBNP)	D0*, 56 post prime D14, 28 post boost

* Only for participants receiving prime vaccination in the study

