7.3. Study groups

A total of up to 270 (+ up to an additional 10%) participants will be enrolled and randomised (1:1:1) as below:

Group	Arm	Prime (Day 0)	Boost (day 56)
	1	BNT162b2	BNT162b2
	2	BNT162b2	BNT162b2 (one-third dose)
	3	BNT 162b2	NVXCov2373

After 29th November 2021, the enrolment of participants who have received their first dose of COVID-19 vaccine in the community will be temporarily suspended. Only participants who have received their first dose of COVID-19 vaccine in the study will be randomised to a second dose. They will be randomised (1:1) as below:

Group	Arm	Prime (Day 0)	Boost (day 56)
	1	BNT162b2	BNT162b2
	2	BNT162b2	BNT162b2 (one-third dose)

Randomisation will be performed at the time of the second dose, and stratified by study site and anti-nucleocapsid IgG status at baseline where available.

The study will be single-blind, i.e. while staff involved in study delivery will be aware of what vaccine schedule the participant is receiving, the participant themselves will remain blinded to their boost vaccine. This blind will be maintained by applying a masking tape over the vaccine syringe as detailed in the study clinical study plan. Laboratory staff will also be blinded to the vaccine schedule received.

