9.6.1.1.6. Safety pause

Given that a) the homologous BNT162b2 vaccine schedule is licensed for use in 12 to 16 year-olds, b) Data from COMCOV2 demonstrates that BNT162b2 prime followed by NVXCoV2373 boost is no more reactogenic than homologous BNT162b2/BNT162b2 and c) employing fractional dose vaccines as the boost dose are expected to be less reactogenic than full dose regimens, there will be no planned safety pause or expedited review of reactogenicity data. Should significant safety concerns arise at any point (e.g. an AESI) then the DSMB will be consulted as appropriate.

9.6.1.2.

Subsequent visits

Follow-up visits will take place as per the schedule of attendances described in APPENDIX A: SCHEDULE OF PROCEDURES. Participants will be assessed for local and systemic adverse events, interim history, review of diaries (paper or electronic) and blood, saliva/ nasal fluid sampling performed at these time points as detailed in the schedule of attendances. Observations and physical exam will be performed as and when clinically indicated.

Vaccination procedures will be as for D0 visit, adapted to the specific vaccine being administered as outlined in the clinical study plan. Scheduling of the second vaccination visit (D56) should be mindful of any planned routine non-COVID-19 immunisation outside the study (e.g. seasonal influenza vaccine), to avoid administration of the study COVID-19 vaccine within a period 7 days before or after the planned routine vaccine. If necessary, in this situation scheduling of the D56 visit can be delayed beyond the specified D56 study window, but must not be brought forward to less than 8 weeks following D0.

If participants experience adverse events which the investigator (physician), CI and/or DSMB chair deem to require further close observation, the participant may be admitted to an NHS

hospital for observation and further medical management under the care of the Consultant on call.

9.6.2. Visits for participants receiving their first dose of COVID-19 vaccine in the community

The screening visit for these participants will include all the procedures for informed consent and eligibility assessment described above (section 9.6.1.1.1 and 9.6.1.1.2) including date of first dose of COVID-19 vaccination in the community.

The screening visit may be combined with the D56 visit, or be scheduled to occur separately, at some time before the D56 visit.

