12.2. Description of statistical methods

A fully detailed statistical analysis plan will be developed and signed by the chief investigator prior to any data analysis being conducted. In brief, the analysis will incorporate the following:

Safety and reactogenicity

All SAEs will be presented for each group using descriptive analyses. Counts and percentages of each local and systemic solicited adverse reaction from diary cards, and all unsolicited AEs, and AEs of special interest will be presented for each group. Comparisons between the arms will be made using Fisher's exact test.

Immunogenicity

Highly skewed ELISA data will be log-transformed prior to analysis. The geometric mean concentration (GMC) and associated 95% confidence interval (CI) will be summarised by computing the anti-log of the mean of the log-transformed data.

The GMRs and CIs post boost will be calculated for each of the heterologous arms when comparing to the homologous arm.

Spike-specific T cell responses (ELISPOT) will be presented as geometric means and confidence intervals, or medians and interquartile ranges if non-normally distributed after log-transformation.

Comparisons of continuous immunogenicity data between different arms or at different time points will be made using a t-test if normal distribution can be rendered after log-transformation. Otherwise, Mann Whitney U test will be used.

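### The pre-boost sample is labelled day 56 for everyone, but its window is day 56–70 for study-primed and open-ended for community-primed participants, so summaries under that label mix prime-to-boost intervals

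*Protocol*

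**What the plan says.** Appendix A has one D56 column with two windows: "Day 56–70 post prime vaccine at D0 or Day 56 + post prime vaccination in community". Section 5 also sets only a minimum of 8 weeks for people primed in the community. The study-primed limit is not absolute either: section 9.6.1.2 lets the visit fall after the window to keep it apart from a routine vaccine.

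The outcome tables attach a single label to this sample. For anti-spike antibody the synopsis gives "D0*, 56 post prime D 14, 28, 132, 236 post boost", and section 6 gives "D0*, 56, post prime D 14, 28, 132, 236 post boost". The asterisk means "Only for participants receiving prime vaccination in the study" and stands on D0, not on 56, so the day-56 label covers both priming routes. Section 7.3 heads the boost column day 56 for every arm.

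On analysis, section 12.2 says: "Comparisons of continuous immunogenicity data between different arms or at different time points will be made using a t-test" (if log-transformation gives normality). It mentions neither interval nor priming route. Section 9.6.2 does collect what is needed, "including date of first dose of COVID-19 vaccination in the community". Section 7.3 states that after 29 November 2021 enrolment of those who had their first "vaccine in the community will be temporarily suspended", and that from then on only study-primed participants are randomised, to arms 1 and 2.

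**The concern.** A reader takes a day-56 GMC as the antibody level about 8 weeks after one dose, and results under a day-56 boost heading as those of an 8-week schedule. Under Appendix A, a community sample taken on day 77, or on day 110, carries the same label as a study sample taken on day 60. If antibody wanes after one dose, the pooled level understates the 8-week value, and the post-boost GMCs belong to a mixture of schedules.

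This bears on a secondary objective (section 6) and on the trial's policy use. Section 5.1 reports the national advice as at least 12 weeks between doses for healthy adolescents. Whether a reported level belongs to about 8 weeks or to 12 weeks and more is therefore what a policy reader needs to know.

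**Working it through.** **1. The plan's own figures.** The protocol gives no waning rate, no expected community share and no expected interval, so there is no stated figure for this point to reproduce. The nearest yardstick is the minimum detectable geometric mean ratio (GMR) in section 12.1: 10^[(1.960 + 1.282) × SD × √(2/90)]. For log10 SDs of 0.4, 0.5 and 0.6 this gives 1.56, 1.74 and 1.95 (noncentral t: 1.56, 1.75, 1.96), against the stated 1.57, 1.75 and 1.96. Those figures are sound. They concern contrasts between arms and serve here only for scale.

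**2. Label against window.**

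| Place | Study-primed | Community-primed |
|---|---|---|
| Sections 3 and 6, sample label | day 56 | day 56 |
| Section 7.3, boost day | day 56 | day 56 |
| Appendix A, window | day 56–70 | day 56 onward, no end |
| Section 9.6.1.2 | may run later in one situation | – |

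The label fits one window approximately and the other not at all.

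**3. How long the community interval could be.**
- From the dates: a first dose on 13 September 2021 (the announcement for all aged 12–17) and a boost on 29 November 2021 give 17 + 31 + 29 = 77 days.
- From the amendment history, used only as evidence about intervals: the late visits were re-timed so that the 28-day post-boost visit would not coincide with the former D140 visit in community-recruited participants. If D140 was counted from the first dose, a visit at day 28–42 after boost falls on it when the boost was at day 140 − 42 = 98 to 140 − 28 = 112. This is an inference. For a boost on 29 November it implies a first dose between 9 and 23 August, before the general recommendation.

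**4. Effect on the pooled level.** Assumptions, none of them in the documents: one-dose half-life h of 45–90 days, study-primed mean at day 63, half of the sample community-primed at day d. The ratio of a community sample to the day-63 level is r = 2^(−(d − 63)/h). The pooled GMC factor is r^0.5.

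| d | r, h = 45 | r, h = 90 | pooled, h = 45 | pooled, h = 90 |
|---|---|---|---|---|
| 77 | 0.81 | 0.90 | 0.90 | 0.95 |
| 98 | 0.58 | 0.76 | 0.76 | 0.87 |
| 112 | 0.47 | 0.69 | 0.69 | 0.83 |

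The pooled GMC is thus 5–10% low at day 77 and 13–31% low over day 98–112. With half-lives of 30–120 days the day-77 factor runs from 0.85 to 0.96.

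**5. Contrasts between arms.** Randomisation takes place at the second dose, when the interval is already settled, so arms randomised over the same period have the same interval distribution in expectation. Arm 3 recruited only up to 29 November 2021, while community-primed participants were also entering. Arms 1 and 2 continued with study-primed participants only. Over the whole trial, arm 3 is therefore expected to hold the larger community share.

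**The case against.** The strongest reply is that Appendix A schedules visits and does not define an analysis set. Section 12.2 is an outline that defers to a full SAP, which is not at hand, and no sentence says that the two routes will be pooled or the interval ignored. The interval is also disclosed: the primary objective speaks of a boost no earlier than 8 weeks, and Appendix A prints both windows. This stands as far as pooling is concerned, which is inferred. A reader might conclude that the plan throws away the first-dose date; the documents do not support that, since the date is collected and the SAP may use it. The mismatch between label and window is nevertheless fixed in the protocol itself.

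Three other stronger readings also fail.
- **The rise after boost is overstated.** The blood is taken at the boost visit and later visits are timed from it, so each participant's change is a true pre-to-post-boost change. No fold-rise endpoint is defined, and overstatement would require the post-boost level not to depend on the interval.
- **The randomised comparison is biased.** For concurrently randomised arms it is not (step 5).
- **The December 2021 look misled the national committee.** Section 12.4 says only that "we will review the sero-status pre-boost as well as all the available immunogenicity data" and that the look is descriptive. Nothing shows how intervals were reported, and that look predates the current version.

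It is also fair to say that the firm date-based bound lies only seven days beyond day 70 and yields a modest shift.

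**Conclusion.** The point holds as a conflict of labelling and reporting. One named time point covers two different windows, one of them without an end, so a GMC or ELISpot summary under the day-56 label describes a mixture of intervals.

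Its size is unknown from the documents. It is about 5–10% in the pooled GMC at the 77-day bound and about 13–31% if intervals reached day 98–112. Both figures rest on the assumed half-life, 50% community share and day-63 mean; the second also rests on reading the amendment note as above. The direction assumes that waning dominates; infections between the doses would work against it. No figure is offered for ELISpot.

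Comparisons within one allocation period are unaffected, as is the 7-day reactogenicity endpoint as far as this sample is concerned. The contrast to watch is any whole-trial comparison of arm 3 with arms 1 or 2, where the interval mix is expected to differ. Its size cannot be derived, because the documents say nothing on how the post-boost level depends on the interval. The change is worth making because it is cheap.

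**What to change.** Change labelling and analysis only, for the remaining and final reports:

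1. Call the sample pre-boost, and reserve the day-56 label for samples taken within day 56–70 of the first dose, whichever the priming route.
2. Report the actual days since first dose by arm and priming route, from the date already collected.
3. Present pre-boost and post-boost GMCs and ELISpot summaries by interval band (day 56–70 and later) or by priming route.
4. For comparisons with arm 3, use participants randomised concurrently, or show the comparison within the same bands.

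The protocol authors should reconcile the Appendix A window with the day-56 labels in sections 3, 6 and 7.3. Nothing here bears on when anyone is vaccinated.

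The cost is a sentence or two in section 12.2 and the SAP, and somewhat wider confidence intervals within each band. No new data are needed.
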